## 2.8 Clinical management

The recent 2022 ACC Expert Consensus Decision Pathway on Cardiovascular Sequelae of COVID-19 in Adults highlighted the lack of evidence based management strategies for vaccine associated myocarditis/pericarditis. The guidelines indicate nonsteroidal anti-inflammatory drugs, colchicine, and corticosteroids may be considered in those with ongoing symptoms. For those with those with rapidly improving symptoms, a normal or improving cTn level, and normal left ventricular ejection fraction, anti-inflammatory medications may not be needed. However, these recommendations are all extrapolated from treatment of myocarditis/pericarditis of alternative etiologies. Whether similar strategies are effective for vaccine associated myocarditis/pericarditis is unknown.

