### 3.2 Secondary objectives

- Describe the spectrum of presentation, severity, and predisposing factors of vaccine associated myocarditis/pericarditis, COVID-19 myocarditis/pericarditis, and MIS-C/A myocarditis.
- Describe the investigations and management of vaccine associated myocarditis/pericarditis in standard clinical practice, including care settings, diagnostic workup, imaging, and treatment.
- Compare the incidence, type, and severity of major adverse cardiovascular events in patients with vaccine associated myocarditis/pericarditis in patients treated/not treated with NSAIDs, colchicine and other contemporary treatments according to standard clinical practice.
- Develop a risk prediction score for MACE in patients with vaccine associated myocarditis/pericarditis.
- Evaluate subsequent vaccination patterns and risk of COVID-19 infection in patients with and without subsequent vaccination after vaccine associated myocarditis/pericarditis.

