### 3.3 Primary endpoints

The primary endpoints for the three primary objectives are:

1. Composite MACE at 30 days post vaccination (preferred by cardiovascular community) and at 42 days post vaccination (preferred by vaccine monitoring investigators) including any of:
  - Death from any cause.
  - Ventricular arrhythmia (ventricular fibrillation or ventricular tachycardia).
  - Heart block (type II or type III block).
  - Heart failure (national guideline criteria).
  - Left ventricular systolic dysfunction (left ventricular ejection fraction [LVEF] <55%).
  - Cardiac tamponade.
2. Recovery of cardiac function in patients with previously documented abnormal cardiac function (LVEF<55% during anytime at baseline), with LVEF increase by 5% from worst baseline measurement.
3. Quality of life, depression, anxiety, and physical activity using validated instruments at baseline, 3 months, 12 months, and annually.
  - 3a. Quality of life: EQ-5D-5L questionnaire for adults or EQ-5D-Y questionnaire for children.
  - 3b. Depression and anxiety data: PHQ-9 and GAD-7.
  - 3c. Physical activity: International Activity Questionnaire.

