### **5. VISIT SCHEDULE AND PROCEDURES**

Consenting patients will be followed up clinically by their regular physician (e.g. Cardiologist, Internist, other physician) in collaboration with their local site-PIs, in accordance with the 2022 ACC/AHA standard of care guidelines for the management of myocarditis.

Patients will be followed at 3 months and 12 months after diagnosis and annually thereafter for up to 3 years. To standardize follow-up timing the date of vaccination will be assigned as the baseline date. However, baseline visit data will be collected from initial presentation and medical contact which is usually the date of diagnosis. This distinction is made because there is a variation between cases in date of vaccination to date of diagnosis/initial presentation.

The case report form variable list (Appendix 7) outlines the essential elements to be collected including demographic data, vaccination status, presenting symptoms, physical examination findings, diagnostic testing (routine laboratory work, electrocardiogram, MRI), treatments, and patient outcomes. Quality of life, depression, anxiety, and physical activity will be measured at baseline, 3 months, 12 months, and annually thereafter using validated instruments: quality of life EQ-5D-5L questionnaire for adults or EQ-5D-Y questionnaire for children; depression PHQ-9 and anxiety GAD-7; physical activity International Activity Questionnaire. These will be conducted at clinical visits or by telephone if no concurrent clinical visit is scheduled.

Baseline data will be collected for all etiologies of myocarditis, but thereafter follow-up visits will only be undertaken for patients with vaccine associated myocarditis/pericarditis, COVID-19 myocarditis/pericarditis, and MIS-C/A myocarditis/pericarditis (i.e. not alternative etiology myocarditis).

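### The treated versus not-treated MACE comparison lets a low LVEF at first contact both steer treatment and count as the outcome, so an inert drug is likely, though not certain, to look harmful

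*Protocol*

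**What the plan says.** Protocol section 3.2, third bullet, undertakes to compare the incidence, type and severity of MACE in vaccine-associated cases "in patients treated/not treated with NSAIDs, colchicine and other contemporary treatments according to standard clinical practice". The first two bullets of that section only describe.

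Section 2.8 reports the 2022 guidance on who receives these drugs: "nonsteroidal anti-inflammatory drugs, colchicine, and corticosteroids may be considered in those with ongoing symptoms". It also reports who may go without: for patients with "rapidly improving symptoms, a normal or improving cTn level, and normal left ventricular ejection fraction, anti-inflammatory medications may not be needed". The same section says it is unknown whether such strategies work in this condition.

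Section 5 says consenting patients are followed "in accordance with the 2022 ACC/AHA standard of care guidelines for the management of myocarditis".

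Section 3.3 defines the outcome as "Composite MACE at 30 days post vaccination (preferred by cardiovascular community) and at 42 days post vaccination". One of its components is "Left ventricular systolic dysfunction (left ventricular ejection fraction [LVEF] <55" per cent. On the clock, section 5 says: "To standardize follow-up timing the date of vaccination will be assigned as the baseline date".

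Section 6.3 leaves the analysis to a statistical analysis plan. The protocol states no restriction, adjustment or separate time zero for this comparison.

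**The concern.** Treatment here follows clinical judgement. Normal LVEF is one of the features that section 2.8 associates with going untreated, and it is the complement of a MACE component. So the not-treated group tends to be short of patients who already meet the outcome when treatment is decided, and the treated group tends to hold them.

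The clock adds to this. Section 4.5.1 requires vaccination within the previous 42 days, so first presentation generally falls inside the 42-day window. A low LVEF found on that day is a MACE dated from vaccination, although it came before any drug.

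Section 2.8 stresses the lack of evidence for managing this condition, and section 2.11 says the findings are meant to inform clinical practice. A contrast tilted by who was treated could be read as evidence against, or for, anti-inflammatory treatment.

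**Working it through.** **The plan's own figures.** Section 6.2 gives only case counts. 283/5.1 million × 38 million = 2,109 (stated 2,094); 54/2.5 million × 38 million = 821 (stated 810); 0.60 × 810 = 486 (stated 486). These reproduce closely. No event rate, treatment rate or effect size is given for this comparison, so every rate below is an assumption.

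**Model.** The drug has no effect. Let f be the share with LVEF <55% at first contact, pL and pN the probability of treatment with low and normal LVEF, and rL and rN the MACE risks in those two strata.

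- Share treated: T = f·pL + (1−f)·pN
- MACE in treated = [f·pL·rL + (1−f)·pN·rN] / T
- MACE in untreated = [f·(1−pL)·rL + (1−f)·(1−pN)·rN] / (1−T)

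**Step 1: only new events count.** Take rL = 20% and rN = 2%, f from 5% to 20%, pL from 90% to 100%, and pN of 40% or 60%.

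| f | pL | pN | Treated | Untreated | Risk ratio |
|---|---|---|---|---|---|
| 5% | 90% | 60% | 3.3% | 2.2% | 1.48 (lowest) |
| 15% | 95% | 60% | 5.9% | 2.4% | 2.48 |
| 20% | 100% | 40% | 8.9% | 2.0% | 4.46 (highest) |

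The true risk ratio is 1.00 throughout. The absolute gap runs from 1.1 to 6.9 percentage points.

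**Step 2: presenting low LVEF also counts, as the definition allows.** Set rL = 1. With f = 10%, pL = 90%, pN = 60% and rN = 2%, T = 0.63.

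- Treated: (0.09 + 0.0108)/0.63 = 16.0%
- Untreated: (0.01 + 0.0072)/0.37 = 4.6%
- Risk ratio 3.4

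The same inputs with rL = 20% give 4.6% v 2.5%, ratio 1.8. Counting the presenting finding therefore adds to the bias but is not its only source.

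**Step 3: weaker and reversed selection.**

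- Weak (f = 5%, pL = 70%, pN = 60%): ratio 1.22 with presenting LVEF counted and rN = 5%; 1.13 with new events only at 20% v 2%.
- Reversed (f = 10%, pL = 40%, pN = 60%, rN = 2%): ratio 0.55 with presenting LVEF counted; 0.71 with new events only at rL = 20%.
- None (pL = pN): ratio 1.00.

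**Step 4: overlap.** Untreated low-LVEF patients = N·f·(1−pL).

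- N = 486: from 0 (pL = 100%) to 486 × 0.20 × 0.10 = 9.7
- N = 1,061: from 0 to 1,061 × 0.20 × 0.10 = 21.2

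**Step 5: effect of restriction.** Among patients with LVEF ≥55% at first contact, both groups have risk rN in this model and the ratio is 1.00. That removes the LVEF part only. Selection on symptoms and troponin is not modelled and would remain.

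**The case against.** The strongest reply is that this belongs to the analysis plan. The bullet is one line, prescribes no crude analysis, and section 6.3 defers the methods. Baseline biomarkers, imaging and symptoms are already collected (Appendices 7 and 8), so a later plan could adjust. That stands for the choice of covariates and method. It does not answer the whole point, because adjustment leaves a pre-treatment finding inside the outcome unless the at-risk set also changes, and adjustment in the low-LVEF stratum may have few untreated patients to work with.

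A reader might infer that guidance fixes who goes untreated. The documents do not support that. Section 2.8 uses permissive wording and ties treatment to ongoing symptoms. It gives no treatment rate for patients with low LVEF. The guidance dates from 2022 and its cited title covers adults, whereas cohort entry starts on December 1, 2020 and children are included. Section 5 names its guideline differently and concerns follow-up. Selection is a tendency here.

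A reader might also infer that the comparison must show harm. Step 3 shows that it need not.

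Finally, one could read the objective drug by drug, so that patients given only corticosteroids fall into the control for NSAIDs and could turn the sign. The bullet can equally mean any listed treatment against none, in which case they do not. The wording leaves the control undefined, but no sign reversal can be claimed from it.

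**Conclusion.** The concern holds in a limited form. The objective, the reported treatment pattern and the MACE definition together allow a low LVEF at first contact to influence treatment and to be counted as the result. The likely direction is apparent harm from an inert treatment.

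The size cannot be known from the protocol. The range of about 1.5 to 4.5 rests on the stated assumptions about low-LVEF prevalence, treatment rates and a 20% v 2% risk of new events. Weaker selection shrinks it and reversed selection turns it round. The overlap counts, about 0 to 10 at 486 cases and 0 to 21 at 1,061, rest on the same prevalence and treatment assumptions.

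One secondary objective is affected. The primary, descriptive MACE incidence is not. The point should be settled before the comparison is run.

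**What to change.** Reword the third bullet of section 3.2 so that the comparison:

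1. is restricted to patients with LVEF ≥55% and no MACE component at first medical contact, and counts only events after that contact;
2. uses no anti-inflammatory drug of any class as the control, with corticosteroid recipients reported as their own group;
3. is adjusted or weighted for severity at first contact, with the covariates named in the statistical analysis plan;
4. is replaced by description, with no treatment contrast, for patients with LVEF <55% or a MACE component at first contact.

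This changes the analysis only and touches no treatment decision. Most of the data are already listed in Appendices 7 and 8. Appendix 7 names drug classes without start dates, but it is a summary list, so check that the case report form records dates for treatment and events.

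The cost is a smaller comparison set, wider intervals and no treatment-effect statement for patients with low LVEF or a MACE component at first contact. Confounding by symptoms and troponin will remain to the extent that adjustment does not remove it, and the report should say so.

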#### **4.10 Retrospective chart review**

The retrospective study will identify previous cases of vaccine associated myocarditis/pericarditis, COVID-19 associated myocarditis/pericarditis, MIS-C/A myocarditis/pericarditis, and alternative etiology myocarditis.

Recruiting clinicians will refer patients presenting with myocarditis/pericarditis since December 1, 2020 to research staff (i.e., the date Health Canada approved the first mRNA vaccine for COVID19). Initial chart review to determine eligibility for the study and subsequent chart review for initial presentation and follow-up time points will be completed. As vaccination for COVID-19 and COVID-19 infections are occurring continually, chart review of eligible patients will follow the same structure as patients identified from December 1, 2020.

The same clinical information as the prospective study will be collected, including presentation, clinical bloodwork, and cardiac imaging. No data will be collected for the purposes of this study that has not already been collected as part of routine follow-ups. Only available data will be extracted. Follow-up data will be extracted from charts using standardized chart extraction forms at 3 months, 12 months, and annually for up to 3 years following the date of diagnosis of vaccine associated myocarditis/pericarditis, COVID-19 myocarditis/pericarditis or MIS C/A myocarditis/pericarditis.

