**7.7 Appendix 7. Data collection variables**

Eligibility	Study inclusion/exclusion criteria Brighton Collaboration case definition criteria
Diagnosis	Myocarditis etiology Brighton Collaboration case definition level
Demographics	Age, date of birth (Month/year), gender, ethnicity Occupation, education, urban/rural Province, city, postal code (3 digit)
Vaccine	Doses 1, 2, 3, 4, 5, additional doses Vaccine type and date
Covid-19 infection	Infections 1, 2, 3, 4, 5, additional infections Date symptom onset Date diagnosis Diagnostic test (PCR, rapid antigen, self-report, other) Symptoms Treatment
Medical history	Cardiovascular risk factors and disease Autoimmune condition Non-cardiovascular disease
Medications	NSAID, colchicine, steroid, PPI, other
Laboratory tests	CBC, renal function Cardiac biomarkers, inflammatory markers
Examination	Vital signs and clinical signs if recorded
Hospitalization	Date admission and discharge Diagnosis Presentation Management
Death	Date Location Cause
Echocardiography	Left and right ventricular function Pericardial
Cardiac MRI	Left and right ventricular function Late gadolinium enhancement
ECG and Holter	Date ECG abnormalities Holter abnormalities Arrhythmia classification
Outcomes	Primary and secondary endpoints

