**7.8 Appendix 8. Schedule of assessment**

Tests/Procedures	Baseline	3 months (+/- 1 month)	12 months (+/- 1 month)	24 months (+/- 1 month)	36 months (+/- 1 month)
Eligibility	x				
Demographics	x				
Diagnosis	x				
Medical history	x				
Hospitalization	x				
COVID-19 infection	x				
Vaccination status	x				
Physical exam	x				
Vital signs	x	x	x		
Clinical symptoms	x				
Medications	x				
Bloodwork	SOC	x ^	x ^		
ECG, Holter, Echo, MRI	SOC	x ^	x ^	x ^	x ^
QOL, EQ-5D-5L	x	x	x	x	x
EQ-5D-Y	x *	x *	x *	x *	x *
PHQ-9	x	x	x	x	x
GAD-7	x	x	x	x	x
International Activity Questionnaire	x	x	x	x	x
Events, concomitant medication	x	x	x	x	x
Outcomes		x	x	x	x

\* questionnaire for children only

^ repeat diagnostic tests if initial test was abnormal

Previous cases will join the study schedule at the nearest scheduled study visit

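### Later vaccine doses and COVID-19 infections, which one secondary objective depends on, are scheduled for collection at baseline only and appear in no listed endpoint

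*Protocol*

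**What the plan says.** Section 3.2 of the protocol includes this secondary objective: "Evaluate subsequent vaccination patterns and risk of COVID-19 infection in patients with and without subsequent vaccination after vaccine associated myocarditis/pericarditis". Section 2.9 adds that members of the national immunization advisory committee are particularly interested in the study's secondary endpoints on subsequent vaccination.

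Section 3.4 lists six secondary endpoints: the components of the composite, atrial arrhythmias, mortality, hospitalization, recurrence and constrictive pericarditis.

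Appendix 8 is the only visit-by-visit schedule. Its rows "Vaccination status" and "COVID-19 infection" are marked at baseline and left blank at 3, 12, 24 and 36 months. Two general rows continue through follow-up: "Events, concomitant medication", which is not defined further, and the outcomes row, which Appendix 7 equates with the primary and secondary endpoints.

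Appendix 7 provides repeat fields for vaccination, "Doses 1, 2, 3, 4, 5, additional doses Vaccine type and date", and similar fields for successive infections, including those known from a rapid antigen test or self-report. It does not say when these fields are to be updated.

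For the chart-review part, section 4.10 plans extraction at 3 months, 12 months and annually, with the limits "No data will be collected for the purposes of this study that has not already been collected as part of routine follow-ups" and "Only available data will be extracted".

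**The concern.** The objective compares infection risk between patients who did and did not receive another dose after their episode. Both variables come into being during follow-up. A schedule that asks for them only at baseline, together with an endpoint list that omits them, gives no site an explicit instruction to collect them later.

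Two things are at stake. First, doses and infections may be missing, which weakens the description of vaccination patterns. Second, if infections are recorded more fully in one group than the other, the comparison is biased and not merely imprecise. Infections found by home test or reported by the patient are the most exposed, because a chart may not hold them unless someone asks. An SAP can define how these dates are analysed, but it cannot recover information that was never requested.

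**Working it through.** The protocol states no figure to reproduce here. The check sets its sections side by side and then illustrates the possible size.

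**1. Timing.** Section 5 takes baseline data from the initial presentation, usually the date of diagnosis. For a new case, a baseline entry therefore cannot hold a later dose or infection. Remote cases join at a later visit (section 5.2, Appendix 8), so their records may contain more history after the episode. The amount of information could thus depend on how a patient entered the study.

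**2. Schedule count (Appendix 8).**

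| Row | Baseline | 3 mo | 12 mo | 24 mo | 36 mo |
|---|---|---|---|---|---|
| Vaccination status | marked | – | – | – | – |
| COVID-19 infection | marked | – | – | – | – |

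Two rows × 4 follow-up visits = 8 cells, of which 0 are marked.

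**3. Endpoint count (section 3.4).** Of 6 items, 0 concern later vaccination or COVID-19 infection. Because Appendix 7 defines outcomes as the primary and secondary endpoints, the outcomes row does not bring them in. Section 2.9 speaks of secondary endpoints on subsequent vaccination, so sections 2.9 and 3.4 do not agree.

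**4. Comparison with other baseline-only rows.** Hospitalization is also marked at baseline only, but it is an endpoint in section 3.4 and so returns through the outcomes row. Medications are marked at baseline only, but concomitant medication is marked at every visit. Vaccination and infection have no such counterpart. Only the undefined word for events could cover them.

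**5. Possible size of the distortion.** The protocol gives no capture rates, so those below are assumptions. Suppose exposure is classified correctly and a proportion *c* of infections is recorded in each group. Observed risk is then true risk × *c*, and

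observed risk ratio = true risk ratio × (*c* with further vaccination ÷ *c* without).

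With a true ratio of 1.00:

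- Capture 60% versus 80%: 0.60 / 0.80 = 0.75.
- Capture 50% versus 90%: 0.50 / 0.90 = 0.56.
- Capture 90% versus 50%: 0.90 / 0.50 = 1.80.
- Equal capture at any level: 1.00, no distortion.

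Missed doses would add misclassification of exposure, which this formula does not include.

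**The case against.** The strongest reply is that a blank cell does not prove non-collection. The baseline rows may describe the index episode, with the general rows for events and outcomes carrying updates. Section 5 calls the Appendix 7 variables essential and names vaccination status among them, and open-ended fields for further doses and infections suggest a running record. Consenting patients have visits or calls at every time point, so the limits in section 4.10 bind only the chart review. The withdrawal options in section 4.13.4 also mention outcome follow-up from administrative data. Other objectives in section 3.2 have no matching endpoint either, and the assumed capture rates say nothing about this study in particular.

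Part of this stands. The intention to collect is plausible, the fields exist, and nothing in the protocol shows that capture would differ by vaccination status. The ratios above are illustrations, not estimates.

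The rest does not close the gap. The pattern in Appendix 8 counts against the general-row reading, because the other baseline-only items mentioned have a follow-up counterpart and these two do not. Administrative data appear only among the withdrawal options, with no statement that they cover doses or infections. The planned visits and calls could collect the information, but the schedule does not ask them to. The descriptive objectives can largely be met from baseline and treatment data; this one cannot.

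**Conclusion.** The concern holds. As written, the schedule gives neither the exposure nor the outcome of this objective a collection point after baseline (0 of 8 follow-up cells), and section 3.4 contains no endpoint for either (0 of 6), contrary to what section 2.9 implies. The inconsistency is certain. Its effect on the results is a possibility: bias arises only if recording differs between patients with and without further vaccination. Under the assumed capture of 50% to 90% per group, a true ratio of 1.00 could appear as anything from 0.56 to 1.80. The effect is confined to one secondary objective and leaves the primary endpoints untouched. It should be fixed, because details not asked for during follow-up may be unrecoverable afterwards.

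**What to change.** In Appendix 8, mark vaccination status and COVID-19 infection at 3, 12, 24 and 36 months. At each point, update the existing Appendix 7 fields: type and date of any new dose, and date and diagnostic test of any new infection. In section 3.4, add two endpoints: any COVID-19 vaccine dose after the index episode, and COVID-19 infection after the index episode. Sections 2.9, 3.2, 3.4 and Appendix 8 will then agree. The analysis of these dates can be left to the SAP.

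The cost is eight marks in two existing rows, two endpoint lines and a few questions per contact. No new form fields are needed, and section 5 already plans a visit or telephone call for the questionnaires at each time point.
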